9.2.4. Key Elements of Analysis Plan

9.2.4.1. Primary Analysis

The primary endpoint is change from baseline in EGG parameters at Week 2, 5, and 8 at each time interval (pre-and 10, 20 and 30 min after water load). The primary endpoint is change in GMA as assessed by EGG parameters: change from baseline of distribution of average power by frequency region (as % of power); change from baseline of ratios of average power post-water load test (post-WLT)/pre water load test (pre-WLT) by frequency region; and change from baseline of percentage (%) of time with the dominant EGG frequencies in the four frequency ranges (bradygastria, normal, tachygastria and duodenal). The primary analyses of the primary EGG parameters will be conducted using mixed-effect model with repeated measures (MMRM). The MMRM model will include the EGG parameter as the dependent variable; treatment group, time interval, visit week, and treatment-by-week interaction as fixed effects; the relevant parameter baseline as covariate; and subject as a random effect.

The primary endpoint of change from baseline in EGG parameters related to VAS of nausea at Week 2, 5, and 8 at each time interval (pre-and 10, 20 and 30 min after water load) will be analyzed using the MMRM method as described above. The MMRM model will include the EGG parameter as the dependent variable (the same EGG parameters as listed above); treatment group, time interval, visit week, and treatment-by-week interaction as fixed effects; the relevant parameter baseline as covariate; VAS of nausea as time varying covariate; and subject as a random effect.

Treatment effects estimates (and associated 95% CI) of albiglutide will be evaluated within this MMRM model as least squares means contrasts relative to exenatide. An unstructured covariance matrix will be used for the MMRM analysis, unless the model does not converge, in which case the covariance matrix will be decided upon model convergence status and the Akaike information criterion.

Part B analysis is further described in the RAP.

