9.2. Part B: Statistical Considerations and Data Analysis

9.2.1. Hypotheses

Hypotheses testing in Part B will be performed for the parameters listed in Section 3.2 to compare albiglutide to exenatide in subjects with T2DM for a treatment period of 8 weeks.

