9.2.2. Sample Size Considerations

9.2.2.1. Sample Size Assumptions

Approximately 62 subjects (31 per arm) will be randomized in a 1:1 ratio to either albiglutide or exenatide. The study will target to have a total of approximately 50 evaluable subjects (25 subject per treatment arm) taking into account the assumed withdrawal rate of approximately 20%. The study is exploratory in nature and there is no similar published work available in the same indication and population to act as a guide. This sample size is based on feasibility and the sample size assumptions may be re-evaluated once Part A results are available.

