9.2.4.2. Secondary analyses

The relative effects of albiglutide compared to exenatide will also be assessed across a number of secondary endpoints. The secondary endpoints are defined in Section 3.2 and include change from baseline in $T_{1/2}$ at Week 5 and 8; change from baseline in kPCD of GE at Week 5 and 8 and at each time interval (45, 90, 120, 150, 180 and 240 min); change from baseline volume of water ingested during water load EGG test Week 2, 5 and 8; and change from baseline of VAS of stomach fullness, hunger, bloating and abdominal pain during the EGG water load test at Week 2, 5, and 8. The secondary endpoints will be analyzed analogous to the primary endpoint using MMRM. In addition, summary statistics (including number of subjects, mean, median, min, max, SD, SE) and graphical displays will be provided.

The overall general safety and tolerability of albiglutide versus exenatide will be evaluated in tabular and/or graphical format and summarized descriptively.

Vital signs, clinical laboratory tests, adverse events (AEs), Gastroparesis Cardinal Symptom Index – Daily Diary (GCSI-DD), and nausea AEs presenting outside the timing of the WLT and GCSI-DD will be assessed using descriptive statistics.

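### Both Part B primary MMRMs omit treatment-by-time-interval, so they cannot give the interval-specific treatment differences that the primary endpoint calls for

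*Protocol*

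**What the plan says.** Protocol Section 9.2.4.1 states the endpoint as follows: "The primary endpoint is change from baseline in EGG parameters at Week 2, 5, and 8 at each time interval". The intervals are pre-load and 10, 20 and 30 minutes after the water load, as in Section 3.2. Section 9.2.1 adds: "Hypotheses testing in Part B will be performed for the parameters listed in Section 3.2", with the purpose of comparing albiglutide with exenatide.

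The model is then written out: "The MMRM model will include the EGG parameter as the dependent variable; treatment group, time interval, visit week, and treatment-by-week interaction as fixed effects". The baseline value is a covariate and subject is a random effect. The second primary model keeps the same fixed effects and adds "VAS of nausea as time varying covariate". Treatment effects are to be least-squares-means contrasts against exenatide, with 95% confidence intervals, from these models. On covariance: "An unstructured covariance matrix will be used for the MMRM analysis, unless the model does not converge".

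For secondary endpoints, Section 9.2.4.2 says: "The secondary endpoints will be analyzed analogous to the primary endpoint using MMRM". One of them is "change from baseline in kPCD of GE at Week 5 and 8 and at each time interval", with six breath-sample times. The symptom VAS is defined per interval in Section 3.2.

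Section 9.2.4.1 refers to the RAP for further Part B detail. The RAP supplied says that it covers Part A only, and it contains no MMRM.

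**The concern.** Time interval enters as a main effect. It shifts both arms alike and leaves the difference between arms unchanged. Treatment is crossed with week but not with interval, so the model has one treatment difference per week.

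This touches the purpose of the test. Section 2.1 presents the water load as the standardized provocation that distends the stomach and induces nausea. Whether the drugs differ before the load, after it, or both is the natural question for such a test. Under the stated model, a difference that appears only after the load is also reported as present before it, at the same size.

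The reach differs by endpoint:

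- Percent power and percent time in each frequency range: all four intervals are forced equal.
- Post-load/pre-load power ratio: naturally defined only after the load, so 10, 20 and 30 minutes are forced equal. The text does not say which intervals are analysed.
- kPCD and symptom VAS: they inherit the constraint by analogy with the primary model.
- Half-emptying time and water volume: no within-test intervals, so not affected.

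**Working it through.** **Inputs.** Three weeks and four intervals, hence 12 cells (Protocol 3.2 and 9.2.4.1). The fixed effects are those of 9.2.4.1. There are 25 evaluable subjects per arm (9.2.2.1: "The study will target to have a total of approximately 50 evaluable subjects"). The documents give no EGG variance or correlation, so every covariance pattern below is an assumption.

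**The plan's own figure.** 50/(1 - 0.20) = 62.5 against about 62 stated, and 62 x 0.8 = 49.6, so it is consistent. The sample size rests on feasibility. There is no power figure to reproduce, and the point does not depend on one.

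**Step 1: which contrasts the model can represent.** For treatment t (0 or 1), week w and interval i, the mean is

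mu(t,w,i) = alpha + tau*t + gamma_i + beta_w + theta_w*t + baseline term.

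The treatment difference is mu(1,w,i) - mu(0,w,i) = tau + theta_w. The index i has dropped out. In the nausea model the VAS term cancels when the arms are compared at equal VAS. Rank of the 12 contrasts:

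| Model | Distinct values | Rank |
|---|---|---|
| As stated, with or without VAS | 3 | 3 |
| + treatment-by-interval | 12 | 6 |
| + treatment-by-interval, week-by-interval and three-way | 12 | 12 |

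The covariance matrix and random subject effect do not alter this, because the fixed effects determine the contrasts.

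**Step 2: what the single weekly value estimates.** Take a true difference of 0 pre-load and d at 10, 20 and 30 minutes in every week, with complete data and equal arms. If the covariance is separable over week and interval, with interval matrix V, generalized least squares weights the four interval differences by V^-1 1 / (1'V^-1 1). The estimate is d(1 - weight on pre-load).

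- Compound symmetry, equal SDs: pre-load weight 1/4, giving 0.75d.
- AR(1) with correlation r: pre-load weight 1/(4 - 2r). For r = 0.6, 1/2.8 = 0.357, giving 0.64d. For r = 0.8, 1/2.4 = 0.417, giving 0.58d.
- Correlation 0.5, pre-load SD s times the post-load SD: the pre-load weight is proportional to (0.8/s - 0.6)/s and the three post-load weights together to 3(0.4 - 0.2/s). For s = 0.7 these are 0.776 and 0.343, so the estimate is 0.343/1.118 = 0.31d. For s = 1.3 it is 0.98d, and for s = 1.5 it is 1.06d.

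If instead all 12 cells share correlation 0.5, with c = 0.5/6.5 = 0.0769, the estimate is

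d x [3 - 9c(1/s + 3)] / [1/s^2 + 3 - 3c(1/s + 3)^2].

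For s = 0.7 this is -0.0659/0.5149 = -0.13d. For s = 1, 1.3 and 1.5 it is 0.75d, 1.25d and 1.35d.

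In each case the same number is reported for the pre-load interval, where the truth is 0.

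**Step 3: simulation check.** This used 25 per arm, 200 replicates, least-squares fits, and assumed differences of 0, 0.8, 0.4 and 0 at the four intervals. At Week 5 the stated model returned 0.286 at all four intervals, and 0.319 with VAS added (the true average is 0.30). The full interaction model returned -0.009, 0.802, 0.408 and 0.027.

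**Step 4: precision and parameter counts.** With equal variances, the ratio of the interval-specific to the pooled standard error is sqrt(1'V^-1 1). Compound symmetry 0.5: sqrt(4/2.5) = 1.26. AR(1) 0.6: sqrt(2.8/1.6) = 1.32. AR(1) 0.8: sqrt(2.4/1.8) = 1.15. An unstructured matrix has 12 x 13/2 = 78 parameters over all cells, and 3 x 4/2 = 6 over three weeks at one interval.

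**The case against.** The strongest reply is that the protocol defines a measurement at each interval and never says in so many words that the treatment contrast is wanted there. Crossing treatment with week alone could be a choice: a weekly effect, with interval as an adjusting factor. The protocol also treats the model as provisional. Sections 4.2 and 9.1.4.2 allow endpoints and their statistical assessment to be refined in the RAP after Part A without an amendment. Part B was exploratory and the study stopped before it. Finally, separate models per interval multiply the output and lose precision, and the extreme values above need unequal SDs.

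Some of this stands. The early stop leaves no consequence for this trial's results. The extra output is real and is counted under the fix. With equal SDs the distortion is 0.58d to 0.75d in the patterns examined.

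The rest does not remove the mismatch. Section 9.2.1 commits to testing the Section 3.2 parameters between arms, and those are listed by interval. If an average over intervals was meant, the text should say so and fix the weights. The fitted value is an average with weights set by an unknown covariance, and a weight can even be negative. The right to refine the model in the RAP was not used for Part B, so Section 9.2.4.1 is the only Part B primary model there is.

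**Conclusion.** The concern holds. As written, both primary models give three treatment differences where the endpoint definition implies twelve (nine for the power ratio if only post-load intervals count). That result follows from the fixed effects and needs no assumption.

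The size of the distortion does rest on assumptions: the shape of the true effect and the covariance. For an effect present only after the load, the reported value is 0.58d to 0.75d with equal variances and -0.13d to 1.35d over the unequal-variance patterns examined. It is reported equally for the pre-load interval.

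This should be corrected before the Part B model is used again. Its practical weight here is limited by termination in Part A.

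**What to change.** In Section 9.2.4.1, or in a Part B RAP:

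- **Preferred:** fit one MMRM per time interval with treatment, week, treatment-by-week, baseline at the same interval, and unstructured covariance over the three weeks. Report the contrast for each week and interval.
- **Alternative:** keep one pooled model, add treatment-by-interval, week-by-interval and the three-way term, and pre-specify a structured covariance. Adding treatment-by-interval alone is the smallest change, but it assumes the same interval profile of the treatment difference at every week.
- **Power ratio:** state that it is analysed at post-load intervals only.
- **Other endpoints:** do the same for the nausea model (VAS from the same interval), for kPCD (one model per breath-sample time, Weeks 5 and 8) and for the symptom VAS.
- **If an average over intervals is intended:** say so in the endpoint and give the weights.

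No extra data are needed. The costs are output and precision. Assuming four frequency regions for each of the three EGG parameter families, the stated plan has 12 x 2 = 24 primary models and 24 x 3 = 72 weekly contrasts. One model per interval gives (16 + 12 + 16) x 2 = 88 models and 88 x 3 = 264 contrasts. kPCD goes from 1 model to 6, and the symptom VAS from 4 to 16. Interval-specific standard errors are about 1.15 to 1.32 times the pooled ones under the patterns assumed. The pooled alternative has 2 x 3 x 4 = 24 fixed-effect columns plus baseline. If left unstructured it would also have 78 covariance parameters for about 50 evaluable subjects, so it risks not converging. The per-interval models need 6 each.

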6.2. Treatment Assignment

Part A:

All subjects in Part A of the study will receive 10 μ g exenatide twice daily for 5±1 days.

Part B:

Randomized treatment assignment will be done via a web-based interactive response (IRT) system (RAMOS NG). Randomization will be centralized and will be implemented based on a randomization schedule generated by Clinical Statistics using RAMOS. Study center personnel will access the IRT to execute each randomization once a subject has

met all prerequisites for randomization and has completed all scheduled screening assessments.

Subjects will be assigned to study treatment in accordance with the randomization schedule. Eligible subjects will be stratified by screening HbA1c value (<7.5% and \geq 7.5%), and background use of OAM (OAM use versus no OAM use). Additional stratification may be added based on the results from Part A.

Subjects will be randomized in a 1:1 ratio to either open label albiglutide or exenatide.

Study centre personnel will receive a randomization notification indicating only the unique subject identifier, the treatment assignment, and the date and time of randomization. Each subject number will be a unique identifier. Once a subject number has been assigned, the number will not be reused even if the subject withdraws before receiving any study treatment.

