9.2.4.3. Exploratory analyses

The exploratory endpoint number and % of subjects with a shift in gastric rhythm status will be summarized descriptively by treatment group. In addition, the number and percentage of subjects by gastric rhythm status will be provided by time interval and visit. The mean and mean change from baseline in average dominate frequency will be summarized using descriptive statistics.

The details of any further planned analyses, including subgroup analysis, will be provided in the RAP. Moreover, the relationship between EGG parameters and FPG and HbA1c will be examined.

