2. SUMMARY OF KEY PROTOCOL INFORMATION

2.1. Changes to the Protocol Defined Statistical Analysis Plan

The study terminated early with a limited number of subjects enrolled in Part A. Therefore, only data listings will be produced for selected data. These are limited in scope compared to the originally planned statistical analysis specified in the protocol amendment 1 [(Dated: June 23, 2016)].

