9.5.3. Listings

Listings					
No.	Population	IDSL / TST ID / Example Shell	Title	Programming Notes	Deliverable [Priority]
1.	All Subjects		Listing of Subjects with Inclusion/Exclusion Criteria Deviations		
2.	All Subjects		Listing of Reasons for Withdrawal from Study		
3.	All Subjects		Listing of Demographics and Baseline Characteristics		
4.	All Subjects		Listing of Race		
5.	All Subjects		Listing of Subjects by Site ID		
6.	All Subjects		Listing of Concomitant Medication by Generic Term		
7.	All Subjects		Listing of All Adverse Events		
8.	All Subjects		Listing of Hematology Laboratory Data		
9.	All Subjects		Listing of Chemistry Laboratory Data		
10.	All Subjects		Listing of Urinalysis Laboratory Data		
11.	All Subjects		Listing of Laboratory Data for Subjects with Any Value of Potential Clinical Concern		
12.	All Subjects		Listing of Liver Functions with Any Value of Potential Clinical Concern		
13.	All Subjects		Listing of Vital Signs		
14.	All Subjects		Listing of GCSI-DD		
15.	All Subjects		Listing of Exposure Data		
16.	Pharmacodynamic		Listing of all EGG endpoints.		
17.	Pharmacodynamic		Listing of Visual Analogue Scale (VAS) Scores (0-100mm scale)		

Listings					
No.	Population	IDSL / TST ID / Example Shell	Title	Programming Notes	Deliverable [Priority]
18.	Pharmacodynamic		Listing of Gastric Emptying 13C Excreted in Breath (kPCD1) Over Time by Treatment and Visit		
19.	Pharmacodynamic		Listing of Time to Half Gastric Emptying (GET1/2) by Visit		
20.	Pharmacodynamic		Listing of Volume of Water Ingested during EGG with Water Load Test		

CONFIDENTIAL
The GlaxoSmithKline group of companies

204879

Division	: Worldwide Development
Information Type	: Reporting and Analysis Plan (RAP)

Title	: Reporting and Analysis Plan for A Randomized, Open-label, Active-Controlled, Parallel-Group, Exploratory Study on the Effects of Repeated Doses of Albiglutide compared to Exenatide on Gastric Myoelectrical Activity and Gastric Emptying in Subjects with Type 2 Diabetes Mellitus
Compound Number	: GSK716155
Effective Date	: 23-June-2017

Description:

- The purpose of this RAP is to describe the planned analyses and output to be included in the Clinical Study Report for Protocol 204879.
- This RAP is intended to describe the exploratory endpoints for the study Part A only.

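### Part B is randomised within HbA1c and OAM strata, but the listed primary and secondary MMRM terms contain neither factor; if the factors are prognostic beyond baseline, reported standard errors are somewhat too large

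*Protocol*

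**What the plan says.** Protocol Section 6.2 sets the Part B strata. "Eligible subjects will be stratified by screening HbA1c value", with a cut at 7.5%, and by a second factor: "background use of OAM (OAM use versus no OAM use). Additional stratification may be added based on the results from Part A". The synopsis and Section 4.3.1 say the same. Two binary factors give four strata.

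Section 9.2.4.1 then writes out the model terms twice. The primary EGG model has "treatment group, time interval, visit week, and treatment-by-week interaction as fixed effects", the baseline of the same parameter as covariate, and subject as a random effect. The nausea-related model has the same terms plus nausea VAS as a time-varying covariate. Neither list contains HbA1c stratum or OAM use.

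Section 9.2.4.2 extends the model: "The secondary endpoints will be analyzed analogous to the primary endpoint using MMRM". In the rest of the Part B analysis text HbA1c appears only in Section 9.2.4.3, where "the relationship between EGG parameters and FPG and HbA1c will be examined". OAM use does not appear at all.

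Section 9.2.4.1 ends by leaving further Part B detail to the Reporting and Analysis Plan (RAP). The RAP supplied as the SAP states in its description: "This RAP is intended to describe the exploratory endpoints for the study Part A only".

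**The concern.** Stratified randomisation balances the arms on the chosen factors, so differences between strata contribute little to the true variability of the treatment contrast. A model without those factors still leaves their variance in its residual. If the factors predict outcome beyond the parameter's own baseline, the reported standard error exceeds the estimator's real sampling variability. Intervals are then wider than the design supports, and a nominal 5% test rejects a true null less than 5% of the time.

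What is at stake is reported precision. With about 25 evaluable subjects per arm, a sample size set by feasibility, and Section 9.1.2.1 looking to Part B for the main assessment of the effect on gastric myoelectrical activity, there is little precision to spare. A further gap is that Section 6.2 allows strata to be added after Part A, and no rule says whether they would enter the model.

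**Working it through.** **Inputs from the protocol.** 62 randomised 1:1 (31 per arm), about 20% withdrawal, 50 evaluable (Section 9.2.2.1); two binary stratification factors (Section 6.2); model terms and 95% intervals (Section 9.2.4.1).

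**The plan's own figure.** 62 × 0.80 = 49.6, about 50. In reverse, 50 / 0.80 = 62.5, which rounds up to 63. The stated 62 is consistent. There is no power, effect size or SD to reproduce.

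**Input not in the documents.** Let R² be the share of post-baseline outcome variance explained by the two factors. No value is given: on sample size, Section 9.2.2.1 says "there is no similar published work available in the same indication and population to act as a guide". R² is therefore varied over an assumed range.

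**Formula.** If the arms are balanced within strata, the residual variance is σ² without the factors and σ²(1 − R²) with them. The ratio of reported standard errors (without / with) is 1/√(1 − R²):

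- R² = 0: 1.000
- R² = 0.05: 1/√0.95 = 1.026
- R² = 0.10: 1/√0.90 = 1.054
- R² = 0.20: 1/√0.80 = 1.118

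**Simulation at the planned size.** There were 20,000 trials per R². Assumptions: HbA1c split 50/50, OAM use 60/40, permuted blocks of 4 within each of four strata, 62 randomised, 50 evaluable at random, baseline slope 0.5, and R² shared equally between the factors. The analysis is a single-week linear model on treatment and baseline, without and with main effects for the two factors. Power is at an assumed difference of 0.8 SD.

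| Quantity | R² = 0 | 0.05 | 0.10 | 0.20 |
|---|---|---|---|---|
| Reported SE, without / with factors | 0.994 | 1.020 | 1.049 | 1.114 |
| Listed model: reported SE / true sampling SD | 0.998 | 1.014 | 1.029 | 1.084 |
| True sampling SD, without / with factors | 0.995 | 1.002 | 1.007 | 1.025 |
| Type I error, without | 4.8% | 4.6% | 4.3% | 3.3% |
| Type I error, with | 4.8% | 5.0% | 5.1% | 4.9% |
| Power, without | 78.0% | 78.1% | 78.7% | 79.6% |
| Power, with | 77.5% | 79.1% | 81.4% | 85.9% |

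The Monte Carlo standard error of a 5% rate is √(0.05 × 0.95 / 20,000) = 0.0015, or about 0.15 percentage points.

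At R² = 0.20 the 11% excess splits into about 8% overstatement of the listed model's own uncertainty and 2.5% real loss of precision (1.084 × 1.025 = 1.111). Most of the loss is therefore in what is reported. The power change from adjusting is −0.5, +1.0, +2.7 and +6.3 points.

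**Second simulation, different assumptions.** 8,000 trials per setting, OAM use 70/30, each of 62 subjects lost independently with probability 20%. The reported SE ratio was 0.99, 1.02, 1.05 and 1.11 at the same four R² values, and 1.19 at R² = 0.30. Type I error of the listed model was 5.1, 4.8, 4.1, 3.1 and 2.7%. Direction and size agree.

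**The case against.** The best defence is that Section 9.2.4.1 gives key elements, not the full model. It defers detail to the RAP, and Sections 4.2 and 9.1.4.2 let statistical refinements after Part A go there without a protocol amendment. The set of strata was itself still open. The RAP is silent on Part B because the study ended first: "The study terminated early with a limited number of subjects enrolled in Part A". That silence does not show a decision to omit the strata. This is fair, and a Part B RAP could have added the terms. But the protocol lists its terms explicitly, twice, and nothing supplied tells an analyst to add the two strata already fixed.

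Second, no harm is demonstrated. The parameter's baseline is already in the model, eligibility limits HbA1c to above 6.5% and at most 9.0%, gastroparesis is excluded, and OAMs are washed out before randomisation. Nothing in the documents supports an R² as large as 20%. This stands, and it limits the size of the claim. It does not show that R² is zero. OAM users stop a drug shortly before baseline and non-users do not, so the two groups could change from baseline differently. That is plausible but not shown.

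Third, the simulation uses one observation per subject, whereas the plan has three post-baseline weeks, four intervals and an unstructured covariance. The exact figures are illustrative, and the degree of conservatism also depends on the assumed block size. The direction does not rest on the single-visit simplification.

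Finally, Part B is exploratory, has no stated power target and did not take place. That lowers the priority but does not make the listed model right.

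**Conclusion.** The point holds. As written, the Part B models ignore the factors used to randomise. The treatment contrast stays unbiased and false positives are not inflated; the error is conservative.

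Its size depends on an R² that the documents do not give. It is nil if the factors explain nothing, about 2% in reported standard error at 5%, about 5% at 10% and about 11% at 20%. Only near 20% is the power gain from adjusting sizeable, at about 6 points for an assumed 0.8 SD difference. These figures rest on the assumed stratum proportions, block size, baseline slope, random dropout and single-visit stand-in.

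No Part B result was affected, so the point concerns the protocol text and any reuse of the design.

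**What to change.** In Section 9.2.4.1, add HbA1c stratum and OAM use, as recorded at randomisation, as fixed effects in both primary models. Add that any stratification factor introduced after Part A will also be included. State in Section 9.2.4.2 that the secondary MMRMs carry the same terms. A Part B RAP would serve equally well.

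The cost is one line of text and two degrees of freedom: in the single-visit stand-in, 50 − 3 = 47 residual degrees of freedom become 45. If the factors prove not to be prognostic, the standard error rises by about 0.6% (1 / 0.994 = 1.006). Each further factor costs at least one more degree of freedom. The two current factors need no new data, because both are already held for randomisation.
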